### Anesthesia and Colonoscopy:

Patients will receive general anesthesia by the ICU or anesthesia team, or, conscious sedation (usually a combination of Fentanyl and Midazolam) by the endoscopist. The choice of sedation will be determined by the primary team, anesthesiologist and/or endoscopist.

Colonoscopies will be performed using Olympus CF-HQ190L and PCF-H190L colonoscopes. The choice of an adult or pediatric colonoscope will be left to the endoscopist's discretion. Each procedure will be performed by a senior gastroenterology fellow under the supervision of a gastroenterology attending. The endoscopy cart nurses will be trained to set up and trouble shoot the Pure-Vu® System. The gastroenterology fellow and attending will receive instructions and training of device use prior to use.

Cleansing success will be attained if a BBPS of  $\geq 2$  is achieved in all segments. Pre and post cleansing photo-documentation will be obtained as well photo-documentation of any bleeding lesion.

A colonoscopy using the Pure-Vu® System will be considered complete if the cecum is reached or bleeding site is found distal to the cecum. A colonoscopy will be considered "incomplete" if the endoscopist elects to stop the procedure for patient safety (patient intolerability, or hemodynamic instability) or technical difficulties. If the endoscopist cannot reach the cecum with Pure-Vu® due to technical difficulties, the endoscopist has an option to use a naked scope to attempt to complete the procedure. If the procedure is incomplete the patient will then undergo standard of care bowel preparation and standard colonoscopy. This will include having the patient consume a bowel preparation at least 4 hours prior to standard of care colonoscopy.

After the procedure, a follow up visit or call will be conducted to check in on the patient's wellbeing. If an adverse event is reported, the adverse event form will be completed and submitted to the IRB.

### Database:

This study will utilize IBM Clinical Connect as the electronic data capture (EDC) system which is a web-based platform maintained by IBM's Standard Operating Procedures. The IBM System has been fully validated according to 21 CFR Part 11 and predicate rules, using a risk-based validation model. IBM is hosted in a SAS-70 Type II certified datacenter located in Raleigh, NC.

Data Processing:

Data will be entered into the database by trained study team members. Any data queries will be resolved and entered into the database. Only Research Coordinators or PIs trained to the use of the database will have access for data entry.

The investigators shall ensure the accuracy, completeness, legibility and timelines of the data reported into the database. Data reported shall be supported by the source documents with any discrepancies being explained. If an item is not available or is not applicable, this fact should be indicated; no space is to be left blank.

Case Report Form:

The Case Report Form (CRF) will be filled up by one of the study team members. The CRF will include questions noted under methodology- variable to be collected and studied.

Post procedure endoscopist/nursing staff satisfaction survey:

Immediately following the procedure, endoscopists (Fellow and attending) and nursing staff will be required to complete the following questions at the time of colonoscopy report completion

- On a scale from 1 to 5, 1 being very unsatisfied and 5 being very satisfied:

For the endoscopist(s): "Did this device enable you to have a successful and satisfactory exam?"

For the nursing staff(s): "Were you satisfied with the loading and unloading process of this device?"

### Adverse Events Form:

If an adverse event occurred in the procedure or reported during the follow up visit or call, one of the study team members will be responsible to fill out an adverse events form.

All adverse events will be immediately reported to the Institutional Review Board.

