## **Clinical and Urgent Colonoscopy Outcomes using the Pure-Vu® Cleansing System in Hospitalized Patients with Lower Gastrointestinal Bleeding: A Single-Center Prospective Pilot Study**

### **BACKGROUND:**

Acute lower gastrointestinal bleeding (LGIB), while generally defined as gastrointestinal bleeding distal to the ligament of Treitz, can be categorized into small bowel and colorectal bleeding, two sites with distinct presentations as well as diagnostic and management options (1). Acute LGIB secondary to a colorectal source usually presents with sudden onset hematochezia with or without acute blood loss anemia and hemodynamic instability, and usually leads to multiple invasive procedures and hospitalizations. It accounts for up to one-third of all hospitalizations related to GIB (2). The current guidelines recommend urgent colonoscopy to be performed within 8 to 24 hours of presentation and after adequate colon preparation to improve visualization and diagnostic/therapeutic yield (1). While studies looking at optimal timing of colonoscopy are limited for patients with acute LGIB, a study comparing 48 patients with diverticular bleeding who underwent colonoscopy after rapid polyethylene glycol (PEG) preparation and within 12 hours of presentation with endoscopic hemostasis compared to 73 controls without endoscopic hemostasis, found a significant improvement in outcomes in the group that underwent hemostasis, including bleeding (0% vs. 53%) and hospital length (median of 2 days vs. 5 days) (3). In another RCT of 100 patients presenting with LGIB, colonoscopy within 8 hours of presentation after rapid preparation lead to a more definite diagnosis compared to patients who underwent elective colonoscopy within 96 hours of presentation (4). Urgent colonoscopy however requires the rapid administration of a large volume bowel preparation over 3-4 hours until the rectal effluent is clear (1). Purge preparation can be challenging in critically ill patients and frequently requires the placement of a nasogastric tube for administration of the preparation which could place the patient at risk of aspiration, poor tolerance, and rarely, electrolyte imbalances (1). Moreover, bleeding can

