**SECONDARY OUTCOMES:**

Secondary outcome measures will include:

- Diagnostic yield defined as the identification of the source of bleed or adequate visibility to rule out a LGIB source
- Therapeutic yield defined as control of bleeding source through endoscopic interventions
- Re-bleeding rate defined as recurrent hematochezia/ bright red blood per rectum within 48 hours of the index colonoscopy with Pure-Vu® system
- Need for repeat colonoscopy within 48 hours of index colonoscopy using Pure-Vu® to control source of bleed
- Length of the procedure
- Endoscopist satisfaction
- Length of intensive care unit (ICU) stay (only applicable if subject had colonoscopy in the ICU)
- Length of hospital stay

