**Variables to be collected and studied:**

- Patients Characteristics and Demographics:

Date of birth, gender, ethnicity, body mass index, American Society of Anesthesiologists classification, surgical history of the abdomen and pelvis.

- Admission Characteristics:

Hospital (CCF) admission date and time, presenting GI Bleeding symptoms (maroon-colored stool, bright red blood per rectum, abdominal pain, etc.), Baseline labs (if available) and labs at the time of LGIB development (hemoglobin, INR, platelet count), last dose of anticoagulation at time of colonoscopy, blood product transfusion

- Procedure Characteristics:

Date of colonoscopy procedure, type of scope used, type of oversleeve used, colonoscopy start time (scope in time), colonoscopy end time (scope out time), colonoscopy completion, reason for colonoscopy non-completion, segment reached if colonoscopy incomplete, desired segment if colonoscopy incomplete (ileum vs. cecum), cecal

intubation, time to cecal intubation, time for device assembly, sedation type, BBPS pre and post Pure-Vu® System, pathologies found and characteristics (including size, location, morphology, etc.), interventions performed and time spent on each intervention

- Follow up and Adverse event collection:

Adverse event (AE) occurring at the time of the procedure will be documented in the AE form. A follow up visit or call will be conducted 24-48 hours after the procedure. The patient will be interviewed by one of the study co-investigators or coordinator and if an adverse event (AE) is reported, the AE form will be completed.

Any adverse events related to the study will be immediately reported to the Institutional Review Board (IRB).

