**Study Procedures:**

Identification of participants:

Patients admitted to CCF intensive care unit or RNF, with acute LGIB will have their chart reviewed by one of the study members to ensure eligibility and eligible patients will be invited to participate in the study. The patient will be introduced to the study and provided with the study information. Consent will be obtained from the patient the day of the procedure prior to any study activities. As previously mentioned, patients unable to provide informed consent will be excluded from the study.

Bowel preparation:

Enrolled patients will not receive any oral bowel preparation but will receive 2 tap water enemas approximately 30-60 minutes prior to the procedure, 15-20 minutes apart. Patients will be required to be *Nulla per Os* for at least 4 hours prior to the procedure to decrease aspiration risk with sedation.

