### Data monitoring:

Data will be collected from the electronic medical record and managed using an IBM platform built by Motus and the Cleveland Clinic team.

Data collection forms including the case report forms, pre and post-procedure patient surveys, post-procedure endoscopist and nursing staff satisfaction surveys, adverse event forms will be completed as described above. The study coordinator will enter the data into the IBM platform. The data collection forms and questionnaires will be stored safely with the study coordinator in the DDSI department.

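### Adverse-event forms depend on the procedure itself or one patient interview at 24-48 hours, so no provision ensures capture of later in-hospital complications or of events in participants who cannot be interviewed

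*Protocol*

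**What the plan says.** Three sections of the protocol govern when an adverse-event (AE) form is filled in, and they agree with one another.

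- Variables to be collected and studied: "Adverse event (AE) occurring at the time of the procedure will be documented in the AE form". Then: "A follow up visit or call will be conducted 24-48 hours after the procedure". The source at that contact is specified, and a reported event leads to a form: "The patient will be interviewed by one of the study co-investigators or coordinator and if an adverse event (AE) is reported, the AE form will" […].
- Anesthesia and Colonoscopy repeats the post-procedure visit or call, with a form if an event is reported.
- Adverse Events Form gives the same two triggers: "If an adverse event occurred in the procedure or reported during the follow up visit or call".

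On data sources, Data monitoring states: "Data will be collected from the electronic medical record and managed using an IBM platform". The same section lists AE forms among the instruments to be completed in the way already described, which leads back to the two triggers.

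The Secondary Outcomes include re-bleeding and repeat colonoscopy, both limited to 48 hours, and two durations that need data up to the end of the stay: ICU stay and "Length of hospital stay".

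**The concern.** The Background notes that guidelines advise against colonoscopy in an unprepared colon, partly because of a higher risk of perforation. This study omits oral preparation and gives two enemas instead. It enrols patients in the ICU and inpatients admitted for other reasons, and permits general anesthesia. Readers will look to it for safety information even though its primary outcome is cleansing adequacy.

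The AE rule relies on what is seen at the procedure and what emerges at one conversation a day or two later. Two kinds of event are left without an assured route to a form: those first recognised later in the same admission, and those in participants who cannot take part in the conversation. The second group is likely to include the most serious outcomes. A report of no adverse events would then mean none seen at the procedure and none reported at one contact, which is weaker than it sounds.

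**Working it through.** The protocol gives no AE rate or capture rate, so there is no planned figure to reproduce. The check is mainly textual.

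**1. Is there a third trigger?** The sections on AE collection, colonoscopy, the AE form and data monitoring were set side by side. None gives an end point for AE surveillance beyond the 24-48 hour contact, names chart review as a way of finding AEs, or names another informant. The case report form is limited to the listed variables, and that list has no item for post-procedure perforation, aspiration or death.

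**2. Would another outcome register the event?** Re-bleeding and repeat colonoscopy stop at 48 hours and describe bleeding, not perforation or pneumonia. Length of stay might be prolonged by a complication but does not identify it. A contact made at 24 hours also ends before the protocol's own 48-hour outcome window.

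**3. When does the assured window close?** Urgent colonoscopy is defined as within 24 hours of presentation, and the contact is at most 48 hours after the procedure:

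24 h + 48 h = 72 h = 3 days from presentation, at the latest.

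The only lengths of stay in the document come from a cited diverticular-bleeding study: "hospital length (median of 2 days vs. 5 days"), for patients with and without endoscopic hemostasis respectively. As scenarios only, and assuming stay is counted from presentation:

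- Median 5 days: 5 − 3 = 2, so at least half of patients would spend about 2 or more days in hospital after the last AE contact.
- Median 2 days: the gap in time is small, and mainly the interview gap remains.

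**4. How much could under-capture matter with 20 patients?** One event is 1/20 = 5%. For illustration, let p be the true proportion of patients with a complication and f the share of these recorded. Both are assumptions. The chance of recording at least one is 1 − (1 − pf)^20:

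| p | f = 1 | f = 0.75 | f = 0.50 | f = 0.25 |
|---|---|---|---|---|
| 5% | 64.2% | 53.4% | 39.7% | 22.2% |
| 10% | 87.8% | 79.0% | 64.2% | 39.7% |
| 20% | 98.8% | 96.1% | 87.8% | 64.2% |

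If none is recorded in 20, the exact two-sided 95% upper limit is 1 − 0.025^(1/20) = 16.8%. That limit applies to the recorded rate pf. Dividing by f gives a limit for the true rate of 16.8% at f = 1, 22.5% at f = 0.75 and 33.7% at f = 0.50.

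**The case against.** The strongest reply has five parts.

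- **A reporting duty exists.** The AE form section sends all adverse events to the IRB immediately, with no limit of time or informant, and the record must be followed to the end of the stay anyway. Staff may well notice a late perforation. This defeats the claim that such events are missed, which a reader might infer. It does not supply the rule: a duty to report known events is not a method of finding them.
- **The interview gap is narrow.** Patients without capacity to consent are excluded, participants must be stable or stabilised, and the contact may be a visit. This stands in part. The gap is confined to participants who deteriorate, remain sedated, die or cannot be reached after consent, and for them no substitute source is named.
- **No AE rate is a listed outcome.** Correct: the hypothesis makes no safety claim, and the primary outcome is untouched. The point concerns any safety statement drawn from the AE forms.
- **Stays may be short.** The 5-day median belongs to controls without endoscopic hemostasis, while the group with hemostasis had 2 days. It would be wrong to infer that half of these patients will have uncovered days.
- **Enema events may already be covered.** The enemas come under Study Procedures: participants "will receive 2 tap water enemas approximately 30-60 minutes prior to the procedure, 15-20 minutes apart". The time of the procedure can reasonably be read to include them, and nothing bars their mention at the interview. A firm claim that collection opens too late is not supported. What remains is that a participant prepared but never scoped has no procedure from which to time the follow-up.

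**Conclusion.** The point holds in a limited form. The protocol fixes two triggers for an AE form and nothing in it ensures capture of complications first recognised in hospital after the 24-48 hour contact, or of events in participants who can no longer be interviewed. AE ascertainment is protocol content, so this is not a detail that can be left to a statistical analysis plan.

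The direction of the effect is toward under-counting. Its size cannot be derived from the document, since neither the complication rate nor the share captured is given. The figures above depend on assumed values and show only that, in 20 patients, a modest loss of capture can turn one event (5%) into none. The document does not support saying that events will be missed, or that an AE rate is biased by a known amount.

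**What to change.** Amend Variables to be collected and studied and Adverse Events Form as follows.

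1. Name medical-record review as an AE source alongside the 24-48 hour interview. Run it from the start of study bowel preparation to the later of hospital discharge or the 24-48 hour contact. Discharge alone would close collection too soon for patients who go home before the call.
2. Complete a form for any event found by either route, including when the participant cannot be interviewed, has died, or was prepared but not scoped.
3. Report procedural events and those up to 48 hours separately from later ones. Follow-up to discharge differs in length between patients, and the split gives a window meant to be common to all. Record the time of the contact, so that anyone whose coverage ended before 48 hours is visible.
4. Reconcile which events go to the IRB immediately: one section says those related to the study, the other says all. With wider collection this determines the workload.

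The cost is a short amendment and modest extra abstraction from a record already followed for length of stay, more for long or complicated admissions. No extra visit is needed and clinical care is unchanged. The AE count may become less favourable.

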### Data monitoring:

Data will be collected from the electronic medical record and managed using an IBM platform built by Motus and the Cleveland Clinic team.

Data collection forms including the case report forms, pre and post-procedure patient surveys, post-procedure endoscopist and nursing staff satisfaction surveys, adverse event forms will be completed as described above. The study coordinator will enter the data into the IBM platform. The data collection forms and questionnaires will be stored safely with the study coordinator in the DDSI department.

### Sample size calculation:

This is a pilot study of 20 patients who will undergo urgent colonoscopy using the Pure-Vu® System for acute LGIB in the intensive care unit or the GI endoscopy suite. Interim analysis will occur after the first 10 patients are enrolled.

## **BUDGET**

The study will be funded by MotusGI Ltd. The company will cover the costs of all the Pure-Vu® System devices used. They will provide free training (on-site if allowed) and virtually to all providers who will be performing colonoscopies using the Pure-Vu® System. In addition they will cover administrative costs, IRB review costs, regulatory documentation for the duration of the

study, close out, project manager and statistics costs, and subject fee (please see budget form attached). In addition, in the rare instance that the initial colonoscopy could not be performed using the Pure-vu device, the sponsor has agreed to pay for the cost of the second colonoscopy performed in the traditional method without the use of the Pure-vu device. All other standard of care costs, including the index colonoscopy procedure (at the time of Pure-Vu® System device is used) will be charged to the patient and/or insurer.

